Cover paper

Research title: (The effect of two and four activations daily of the periodontal distractor on pain intensity and pulp vitality of maxillary canine: Randomized Clinical Trial)

Study Start: February 1, 2021 [Actual]

Primary Completion: August 1, 2022 [Actual]

Study Completion: October 15, 2022 [Actual]

Objectives:

Since the periodontal distractor may cause some degree of suffering for the patients and may affect pulp vitality, Therefore the aim of the present study was to evaluate the effect of twice and four activations day of periodontal distractor on pain intensity and pulp vitality of maxillary canine.

Methodology:

PICO:

- Problem: orthodontic patients that have
 - (1)Class I malocclusion severe crowding or bi maxillary protrusion
 - (2)Class II div 1 malocclusion.
- Intervention: performing bilateral maxillary 1st premolar extraction, inter septal bone cuts then placing periodontal distractor and activate it till complete canine retraction.
- Comparison: two versus four activation per day.
- Outcomes:
 - Pain intensity.
 - Pulp vitality.

Study design

The study was randomized control study. It was conducted in a sample of 32 canines on 16 female patients attending the Faculty of Dental Medicine for Girls, Al Azhar University, seeking for orthodontic treatment. Their age was ranged from 16 to 22 years. This prospective study was approved by Research Ethic Committee (REC), Faculty of Dental Medicine for Girls, Al Azhar University with this code (REC-OR-21-01) Fig. (8) Showing CONSORT 2010 flow diagram of this study.

All study participants have signed on written informed consent prior to enrollment. The steps of the study, the aim, the potential benefits, and hazards, all were discussed with the patients.

Sample size calculation:

To Compare the effects of two different orthodontic treatment modalities on pain; independent t test was used for comparison between groups. According to a previous study by Raza et al (2021), Mean VAS scores were 16 ± 3.94 (24 hours) at control side, in comparison to 46.50 ± 6.69 (24 hours) A minimum total sample size of 6 samples on each group are sufficient to detect the effect, by increasing 2 patients on each group to overcome dropping out of patients, the number were 8 on each group and 16 on both groups (fig 1).

Patient Records

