Inclusion criteria were: 1-Orthodontic Patients need extraction of first permanent premolar for orthodontic reasons (dentoalveolar maxillary protrusion, Class II div 1 malocclusion), 2-No history of previous orthodontic treatment, 3- Absence of any systemic disease, 4- Good oral hygiene and healthy gums look, with no signs of redness, edema, or bleeding during brushing (periodontal inflammation), 5- Highly motivation and cooperation

Exclusion criteria were: 1- Medically compromised patients, -2-Use of medication that may affect tooth movement during the period of the study.

After patient selection, routine records of all the patients such as a detailed case history, pretreatment study model, extraoral and intraoral photographs, panorama and lateral cephalometric radiographs were acquired. Pain intensity and discomfort was evaluated at different times by Visual Analogue scale (1st 48 hour after intervention, during each activation of the distractor, and on the Interval between activation) as research related records. Electric pulp testing of canine was done before and after retraction to evaluate pulp vitality.

All the patients in the study required bilateral first premolar extraction. They were divided into two groups (Group I): Canine retraction was done by periodontal distractor with twice activations per day. (Group II): Canine retraction was done by periodontal distractor with four activations per day.

Randomization Allocation concealment:

Randomization was accomplished using online research randomizer. Numbers were from 1 to 16 and each group contained 8 numbers. Set 1 of numbers was assigned to periodontal distractor with two activations per day. Set 2 of numbers was assigned to periodontal distractor with four activations per day. The randomized numbers for the participant were written in opaque white papers which were folded, codes for randomization were kept with another investigator. Allocation of each patient to either group was done by picking up by a colleague with allocation ratio 1:1.

Study phases: This study included four phases:

Phase I: Posterior segment leveling and alignment:

For patients of both groups the orthodontic treatment was started with direct bonding of Roth brackets (Dynaflex,USA) to the maxillary canine, second premolars first molar only. Sectional nickel titanium (NiTi) arch wires were used starting from

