0.014" up to stainless steel arch wire 0.016"×0.022". This was undertaken to align the posterior segment before premolar extraction to allow proper placement of distractor without canting. Fig. (1).

Figure (1) After leveling and alignment of posterior segment with sectional wire.

Phase II : Extraction and inter septal bone corticotomy phase.

Patients were referred to the clinic of Oral and Maxillofacial Department, Faculty of Dental Medicine for Girls, Al Azhar University to extract first maxillary premolars with written referral note. The post extraction instructions were firm and clear not to use NSAIDs drugs for analgesia, paracetamol drugs were prescribed¹.

The second step consisted of performing corticotomies (grooves) in the interseptal bone distal to the canine with bur. Initially, two vertical grooves were done inside the extraction socket, along the buccal and lingual sides then, another groove that was extended obliquely toward the base of the interseptal bone to weaken its resistance Fig. (2). The depth of the undermining grooves was dependent on the thickness of the interseptal bone, as revealed on the Periapical films that was done immediately after extraction . Corticotomy was done by surgical bur on straight hand piece (Apple dental, china) using normal saline for irrigation to prevent adverse thermal changes in the periodontium.

Fig. (2) Inter septal bone Coricotomy with surgical bur on straight hand piece

Phase III: Periodontal distractor construction and placement:

A Hyrax screw(Dentauram, Germany) was modified to form a distractor. Bands on molar and canine were placed with a lingual button welded for the attachment of the elastomeric chain, to counteract any rotation force that was encountered by the canine during the distraction process.

The screw was opened slightly more than the width of premolar to be extracted and extended arms were bent to desirable shape to be soldered on molar and canine bands. The distractor was placed and cemented by glass ionomer cement Fig. (3).

[figure not shown]

Fig. (3) Steps of periodontal distractor appliance construction from hyrax screw.

Phase IV: Activation of periodontal Distraction Fig. (4) :

Group I : The canine was distracted two per day for a total about 0.4 mm per day.

Group II: four activations of 0.2 mm each for a total about 0.8 mm per day.

The distractor was activated till the distal surface of canine became in contact with the mesial surface of second premolar Fig. (5).

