The patients were instructed to apply orthodontic wax on the superior edges of distractor immediately after its placement to minimize discomfort of the oral mucosa as a result of trauma and friction between mucosal tissue and the distractor.

Fig. (4) Activation of periodontal distractor with key

Fig. (5) Before and after complete canine retraction by periodontal distractor

Measurement of pain: Pain intensity and discomfort was evaluated at different times by Visual Analogue scale (1st 48 hour after intervention, during each activation of the distractor, and on the Interval between activation) Fig. (6) .

[figure not shown]

Fig. (6)Visual Analogue scale of pain.

Measurements of Pulp vitality:

The distracted canine's pulp was recorded with noninvasive, simple and clinically popular device. It was electric pulp tester.

The tip of the probe of EPT (Denjoy, china) was applied on sound enamel on the midpoint of each tooth. This area is the most effective site for EPT because of its close proximity to the highly innervated area of canine crown and because it provides a readily reproducible position. An interface medium as tooth paste was placed on tooth after its dryness with air spray to conduct electrical impulses to the tooth. The device has a numeric scale, and these numbers have been used to register changes in test responses Fig. (7).

[figure not shown]

Fig.7 : Measurement of pulp vitality with electric pulp tester.

[figure not shown]

Fig. (8) CONSORT 2010 flow diagram of patients' recruitment and follow-up

Statistical analysis:

Comparison between different intervals was performed by using Friedman's test (non-parametric data). Comparison between both groups was performed by using Mann Whitney's test (non-parametric).

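### Must the plan state a time index for the Mann-Whitney pain comparison, given that Group I's distraction lasts about twice as long as Group II's?

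*Combined protocol and SAP*

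**What the plan says.** Under Phase IV (activation), Group I's rule is "The canine was distracted two per day for a total about 0.4 mm per day" and Group II's is "four activations of 0.2 mm each for a total about 0.8 mm per day". Both stop on the same anatomical event: "The distractor was activated till the distal surface of canine became in contact with the mesial surface of second premolar". No number of days is fixed and no travel distance is given in millimetres.

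The Measurement of pain section names three periods for the VAS: "1st 48 hour after intervention", and then "during each activation of the distractor, and on the Interval between activation". The later occasions are thus defined by activations, not by days.

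The Statistical analysis section has two sentences. One gives Friedman's test across intervals that it does not define. The other begins "Comparison between both groups was performed by using Mann Whitney" and names no day, activation number, mean, peak or total. The only pain figures in the document, in the Sample size calculation, are 24-hour scores from a cited study.

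**The concern.** After the first 48 hours, pain readings follow activations, and activations run at different daily rates in the two arms. Activation 20 falls on day 10 in Group I and day 5 in Group II. All patients have an extraction and bone cuts before activation, so some of the pain may be surgical and may fade with time. If so, matching by activation number, or averaging over the whole course, sets later Group I days against earlier Group II days. A Mann-Whitney test could then favour two activations a day even if the schedule made no difference on any given day.

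At stake is what a p-value for the first listed outcome means: pain at a given time, pain per activation, or pain over the whole course.

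**Working it through.** **1. Duration (plan's figures).** Group II: 4 × 0.2 = 0.8 mm/day, as stated. Group I: 2 × 0.2 = 0.4 mm/day, as stated, if its step is also 0.2 mm. For equal travel L the duration ratio is (L/0.4)/(L/0.8) = 2.0, whatever L is. At an assumed 6, 7 or 8 mm this is 15, 17.5 or 20 days against 7.5, 8.75 or 10. The number of activations is the same in both arms: 7/0.2 = 35. The mean reading day at 7 mm is 18/2 = 9.0 against 18/4 = 4.5.

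**2. Mean per activation (assumed model).** Take pain at day t since surgery, as a fraction of its starting value, as s·exp(−t/τ) + (1 − s). Here s is the share of pain that is surgical, and t = delay + k/2 (Group I) or delay + k/4 (Group II) for activation k. Assumed, not in the documents: 7 mm travel, τ of 3 to 5 days, delay from surgery to first activation of 0 to 7 days, and s of 0.5 or 1. The starting VAS of 46.5 is borrowed from the sample-size text. The schedule has no effect on any given day.

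Example (s = 0.5, delay 0, τ = 3): the means over k = 1 to 35 are 0.5785 and 0.6555. The difference of 0.077 × 46.5 = 3.6 points compares with 46.5 − 16 = 30.5 points used for sample size.

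Rejection rates below are for a two-sided 5% Mann-Whitney test with 8 per arm. SD 5.49 = √((3.94² + 6.69²)/2) comes from the sample-size text; SD 14 is an assumed larger value. Ranges cover τ = 3 to 5.

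| s | Delay (days) | II minus I (VAS points) | Rejection, SD 5.49 | Rejection, SD 14 |
|---|---|---|---|---|
| 0.5 | 0 | 3.6–4.6 | 23–32% | 7–9% |
| 0.5 | 2 | 1.8–3.1 | 9–16% | 6% |
| 0.5 | 5 | 0.7–1.7 | 6–8% | 5% |
| 0.5 | 7 | 0.3–1.1 | 5–6% | 5% |
| 1 | 0 | 7.2–9.2 | 66–84% | 15–22% |
| 1 | 2 | 3.7–6.1 | 22–52% | 7–12% |
| 1 | 5 | 1.4–3.4 | 6–20% | 5–6% |
| 1 | 7 | 0.7–2.3 | 4–11% | 3–4% |

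With no fading, rejection is 5%. A second set of assumptions (all pain fading from the first day with half-life 4 or 8 days, start 50, between-patient SD 10, within-patient SD 8, travel 5 to 8 mm) gave 45–97% for the whole-period mean.

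**3. Total burden (same model).** Integrate pain over T days of distraction: s·τ·exp(−delay/τ)·(1 − exp(−T/τ)) + (1 − s)·T, with T = 17.5 or 8.75. For s = 0.5, delay 0, τ = 3: (1.496 + 8.75)/(1.419 + 4.375) = 10.246/5.794 = 1.77, higher in Group I. Over the grid the ratio is 1.74–1.97 for s = 0.5 and 1.05–1.17 for s = 1. With no fading it is 17.5/8.75 = 2. So the sign depends on the summary, and burden differs between arms even when pain does not fade.

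**4. Common window of days.** For 5 days at 7 mm, Group I keeps 10 of 35 readings (71% dropped) and Group II keeps 20 of 35 (43% dropped). The residual difference is at most 1.9% of initial pain. Displacement is then 5 × 0.4 = 2.0 mm against 5 × 0.8 = 4.0 mm. For 7 days, 60% and 20% are dropped, the residual is at most 1.6%, and displacement is 2.8 against 5.6 mm.

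**The case for a change.** The strongest case for a change is this. Pain is the first listed outcome and the basis of the sample size. The summary can reverse the direction of the result, so leaving it open lets an analyst choose after seeing the data. A sentence naming the readings, the summary and the index would cost almost nothing.

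Much of that stands. The omission is in the text, and it covers the first 48 hours as well: no summary is named there, and since the PICO list puts surgery, placement and activation together as the intervention, even the start of that clock can be read in more than one way. The 2:1 ratio and the reversal of sign also stand.

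Three things do not carry over:

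- **The rejection rates are not false-positive rates for the stated aim.** The Objectives ask how two versus four activations a day affect pain intensity, without fixing a day. A shorter course is part of what was randomised, so a difference in whole-course pain is a genuine consequence of the schedule.
- **The high rates need extreme inputs.** The 84% requires no delay, τ = 5, the small SD and wholly surgical pain; the 97% also lets all pain fade from the first day. Neither sits well with the plan's own premise, "Since the periodontal distractor may cause some degree of suffering for the patients". The SD of 5.49 describes 24-hour scores in another study, not whole-course patient means.
- **Day-matching is a trade-off.** It equalises time since surgery but not displacement, discards many readings, and needs dated entries that the documents do not mention. Reconstructing days from activation number would rest on an adherence assumption.

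**Conclusion.** No change to the plan follows. This is a gap that analysts can fill sensibly: the Measurement of pain section already names the periods, the natural reading is one group comparison per period, and nothing rules out a day-matched look. Per-activation mean and total burden are both valid randomised comparisons. What they need is a clear label in the report, alongside the distraction duration.

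The firm figure is the nominal duration ratio of 2.0, which assumes equal travel and full adherence to the stated rates. The effect on inference is not established. With half the pain surgical and a delay of 5 to 7 days, the whole-course mean shifts by 0.3 to 1.7 VAS points and rejection is 5–8%; other assumed inputs reach 84% or 97%, and total burden shifts the other way. No single index is clearly better, and the trial was completed in October 2022, so an index chosen now would not be a prespecified one.

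### No VAS is listed just before the first activation, and the start of the 48 hours and of activation is undefined: surgical pain adds noise, though not bias, to the two-versus-four comparison

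*Combined protocol and SAP*

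**What the plan says.** - **When pain is measured.** Patient Records and Measurement of pain give the same three occasions: "1st 48 hour after intervention, during each activation of the distractor, and on the Interval between activation". Neither section lists a VAS before surgery or just before the first activation. Pulp testing, by contrast, has a reading before and after retraction.
- **What the 48 hours follow.** The PICO describes the intervention as "performing bilateral maxillary 1st premolar extraction, inter septal bone cuts then placing periodontal distractor and activate it till complete canine retraction". That covers several steps, and no section says which one starts the 48 hours or how long after surgery activation begins.
- **What the arms share.** "All the patients in the study required bilateral first premolar extraction". The extraction and corticotomy text (Phase II) has no arm-specific wording, and nor does the analgesia instruction, "not to use NSAIDs drugs for analgesia, paracetamol drugs were prescribed". Surgery could differ between patients, though: "The depth of the undermining grooves was dependent on the thickness of the interseptal bone".
- **Where the arms differ.** Only in Phase IV. For Group I, "The canine was distracted two per day for a total about 0.4 mm per day". Group II has four activations of 0.2 mm, about 0.8 mm per day.
- **Allocation and analysis.** "Allocation of each patient to either group was done by picking up by a colleague with allocation ratio 1:1". Under Statistical analysis, "Comparison between both groups was performed by using Mann Whitney's test (non-parametric". No baseline adjustment or change score is mentioned.

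**The concern.** The objective is the effect of activation frequency on pain, but every patient first has an extraction and bone cuts. Without a reading at the moment the arms begin to differ, nobody can say how much of a patient's later VAS is leftover surgical pain, how much is that patient's general way of scoring pain, and how much is activation.

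Two things are at stake. The first is precision, because with 8 patients per arm any avoidable between-patient spread is expensive. The second is interpretation. If activation had not begun, the 48-hour comparison sets two identically treated groups side by side, and a non-significant result there could be misread as showing that four activations hurt no more than two.

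**Working it through.** **1. The plan's own effect size.** Sample size calculation gives 16 (SD 3.94) and 46.50 (SD 6.69).
- Difference: 46.50 − 16 = 30.5.
- Pooled SD: √((3.94² + 6.69²)/2) = √30.14 = 5.49.
- d = 30.5/5.49 = 5.56.

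Alpha, sidedness and power are not stated. At two-sided 0.05, a t test reaches 80% to 99% power with 3 per group (noncentral t: 0.789 with 2 per group, 0.998 with 3). The plan's 6 per group is therefore not reproduced at these settings, although 6 in total would be. The present point does not depend on that. With 8 per group at d = 5.56, power is about 100% with or without adjustment.

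**2. Does shared surgical pain bias the comparison?** Write a patient's VAS at a given time as S + A + e, where S is surgical pain, A the activation effect of the arm and e residual error. S has the same distribution in both arms, because the surgery is the same and patients are randomised. The expected arm difference at matched times is therefore the difference in A alone.

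A simulation agrees (5,000 runs, 8 v 8, exact Mann-Whitney). Its assumptions are a true difference of 10 points, residual SD 5.49, and a pre-activation VAS with error SD 2.7:

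| Surgical-pain SD (assumed) | Mean difference, no baseline | Power, no baseline | Power, pre-activation VAS subtracted |
|---|---|---|---|
| 0 | 9.95 | 0.91 | 0.83 |
| 5 | 10.02 | 0.69 | 0.83 |
| 10 | 10.05 | 0.37 | 0.83 |
| 20 | 9.67 | 0.13 | 0.83 |

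With a true difference of 0, the unadjusted false-positive rate was 0.050 to 0.053. The estimate stays near 10 and the error rate holds. What falls is power.

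**3. Chance imbalance.** The SD of the difference in mean surgical pain is S-SD × √(1/8 + 1/8) = 0.5 × S-SD. If the surgical-pain SD is 10, this is 5 points, and an imbalance above 5 points occurs in about 32% of trials. Without a pre-activation reading it cannot be corrected.

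**4. What adjustment buys.** Adjusting for a covariate with correlation r divides the residual SD by about 1/√(1 − r²). An assumed 1.5 SD difference then acts like 1.5/√0.75 = 1.73 SD at r = 0.5 and 1.5/√0.51 = 2.10 SD at r = 0.7. Simulated power, 8 v 8:

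| r (assumed) | Mann-Whitney, activation readings | Rank ANCOVA on pre-activation VAS |
|---|---|---|
| 0 | about 77% | about 75% |
| 0.3 | about 76–78% | within about one point of unadjusted |
| 0.5 | about 78% | about 84% |
| 0.7 | about 78% | about 93% |

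Type I error of the rank ANCOVA was about 5%.

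**5. The 48-hour window under each timing.**
- *Activation after 48 hours:* the arms have been treated alike, so the group test rejects about 5% of the time whatever the effect of activation.
- *Activation from the start of the window:* two days hold 2 × 2 = 4 activations in Group I and 2 × 4 = 8 in Group II, on top of the same surgical pain.

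**6. A conditional route to bias.** Suppose readings are pooled over all activations and activation starts right after surgery. For an assumed travel of 6, 7 or 8 mm at 0.2 mm per activation, each arm has 30, 35 or 40 activations. The first 48 hours then supply 4/30, 4/35 or 4/40 (13%, 11%, 10%) of Group I's readings and 8/30, 8/35 or 8/40 (27%, 23%, 20%) of Group II's. Early surgical pain would weigh more heavily in Group II.

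**The case against.** The strongest reply is that randomisation has already dealt with surgical pain. It is shared, it cancels in expectation, and the unadjusted test is valid. That stands. A reader might infer that surgical pain contaminates the two-versus-four contrast, but the documents describe the same surgery in randomised arms, so they support lost precision only. Pooling readings as in step 6 would be an exception, and the plan does not say that it does so.

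A reader might also infer that surgical pain can never be removed. That fails if activation began after 48 hours, because the 48-hour VAS is then itself a pre-activation reading and can serve as the covariate.

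A third tempting reading is that the 48-hour window dilutes the pain outcome. Averaging it equally with the activation readings would cut power at 1.5 SD to about 32–39%. No section says the windows are averaged, and the Friedman test across intervals suggests they are kept apart. That figure should not be charged to the plan.

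Finally, the 1.5 SD difference and the correlations are assumptions, and at the plan's own d nothing is gained. This limits the size of the point. It does not remove it, because the correlation is unknown and the planning difference comes from another study. If surgical pain with SD 20 came on top of the 5.49, the same 30.5 points would be 30.5/√(5.49² + 20²) = 30.5/20.74 = 1.47 SD.

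**Conclusion.** The point holds as one of precision and interpretation, not of bias. The documents list no VAS immediately before the first activation, plan no adjustment, and leave both the 48-hour origin and the start of activation undefined. Surgical and activation pain therefore cannot be told apart within a patient unless a recorded VAS happens to precede the first activation.

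The loss ranges from nothing (at d about 5.6, or with a correlation near zero) to about 6 points of power at r = 0.5 and 15 points at r = 0.7, for an assumed 1.5 SD difference with 8 per arm. If activation followed the 48-hour window, a between-group result on that window carries no information about activation frequency. These conclusions assume normally distributed scores in the simulations and the same interval from surgery to activation in both arms, which the documents neither state nor contradict.

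**What to change.** 1. State which step starts the 48 hours and when the first activation took place in each group.
2. Take one VAS mark in both groups immediately before the first activation. Compare the groups on readings from first activation onward, at matched times, adjusted for that mark by rank ANCOVA.
3. The cover page gives the study as complete on October 15, 2022. For existing data, use as covariate the last VAS recorded before first activation, where one exists.
4. If the 48-hour VAS precedes activation, treat it as post-surgical pain: report it descriptively or use it as the covariate, and do not use it as evidence on two versus four activations. If activation began inside that window, report it separately and do not pool it with later readings.

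The cost is one VAS mark per patient in a future protocol, a sentence in the analysis section, and one residual degree of freedom. The last costs about 2 points of power if the correlation is zero. For the completed trial no new data are needed.
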